11. Clinical assessments above are a minimum for trial purposes only and do not represent the entirety of necessary medical care. Weekly treatment visits occur once every 5 treatment fractions during radiation. Follow up visits should be scheduled per standard of care and physician discretion. Per NCCN guidelines, clinical follow up visit should occur 1-4 times per year with continued annual mammograms.
12. Identified patients who voluntarily agree to complete the Health Care Expense Survey should be provided this survey at 2-8 weeks post standard of care hypofractionated radiation. (See section 8.4 Economic Analysis for further instruction)
13. Patients who volunteer to complete the Health Care Expense Survey must be provided with the Informed Consent Letter prior to completing the questionnaire.

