For comparison assessment, this survey will be administered to an additional 45 patients undergoing standard of care hypofractionated radiation who are otherwise not eligible or interested in enrollment on this protocol. The Health Care Expense Survey should be provided to the patient and completed by the patient 2-8 weeks post standard of care hypofractionated radiation. The comparison group will either receive a \$20 meal card or be reimbursed for a meal up to \$20, with provision of a receipt from the date of the study visit, after completion of the Health Care Expense Survey. This comparison cohort will be case-matched for distance to treatment facility and employment status.

Collected 2-8 weeks after the completion of radiation:

- Work status prior to breast cancer diagnosis (job for pay or business owner, not including work around the house; including work in a family farm or business even if unpaid).

Protocol name: NOVEMBER (Novem- (9), BrEast Radiation), A Phase II trial of a 9 day course of whole breast radiotherapy for early stage breast cancer.

Version Date: 23NOV2021

Principal Investigator: [name]

- If working number of days working per week.
- If working, number of hours working per day.
- Profession and the job title.
- Total number of hours spent for each radiation treatment (time from leaving home or work to return to home or work).
- Distance from radiation treatment facility from home or work.
- Means of getting to radiation treatment facility (ask if only one modality used or a combination, if a combination record number of days for each modality).

1) Car

- Approximate cost for parking
- Did patient drive, was patient driven, or a combination

2) Shuttle

- Approximate cost

3) Public transportation

- Approximate cost per visit

4) Foot

5) Taxi/car service

- Approximate total cost per visit (both ways)

- Number of radiation treatments during which at least one other person accompanied patient

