### 9.2.4 Economic Analysis:

Cost-effectiveness (CE) analysis of hypofractionated radiation versus standard fractionation will be explored using cost data and quality adjusted life years (QALYs) (i.e. effectiveness side). A societal perspective will be applied for the analysis because the direct costs (i.e. resource used) relevant to treatments/intervention, indirect costs (i.e. resource lost such as travel time, lost productivity) and side-effects related costs will be considered. Cost for the intervention will be measured for the cost of therapy, medications, hospitalization and medical visits. Costs for treatments due to side effects will be collected. Patient times spent for treatment, travel and lost productivity will be converted to costs using year 2022 mean adult US wage rate. Because costs related to the intervention will be occurred in different years (for example, 2018~2022), they will be adjusted to year 2022 US dollars using the medical component of the Consumer Price Index. If charged amounts relevant to the treatments are available only (i.e. plan paid amounts or reimbursed amounts are not available), they will be converted to costs by using cost-to-charge ratios. We will not compare charges or costs between institutions. The quality of life (QoL) measures will be based on the BREAST-Q and EQ-5D survey and will be used to calculate Quality Adjusted Life Years (QALYs) for the effectiveness side. Because costs and effects will be measured over multiple years, both costs and effects will be discounted at the rate of 3.5%. We will utilize the EQ-5D and Breast-Q to assist in the QALY analysis. See appendix IV. Once parameters are computed: 1) mean differences in cost and effect between treatments, 2) variances for differences in costs and effects, and 3) covariance between effectiveness and cost difference, the incremental cost-effectiveness ratio (ICER) or incremental net benefits summarizing the monetary value of the intervention will be calculated.

$$ICER = \frac{Cost_{\text{Hypofractionated Radiation}} - Cost_{\text{Standard Fractionation}}}{Effect_{\text{Hypofractionated Radiation}} - Effect_{\text{Standard Fractionation}}}$$

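### The exploratory cost-effectiveness analysis needs a QALY difference and a cost-effect covariance, but the 45 comparison patients supply cost data only and no other utility source is named

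*Combined protocol and SAP*

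**What the plan says.** Secondary objective 1.2.4 covers patient costs and quality-adjusted life years, with the Breast-Q and EQ-5D as instruments and unspecified historical controls as comparator.

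Section 9.2.4 states that a cost-effectiveness "analysis of hypofractionated radiation versus standard fractionation will be explored using cost data and quality adjusted life years". It lists the parameters to be computed first: the mean differences in cost and effect, their variances, and then "covariance between effectiveness and cost difference, the incremental cost-effectiveness ratio (ICER) or incremental net benefits". An acceptability curve, Monte Carlo simulation with a normal distribution for effects, and one-way ranges over 95% confidence intervals follow. QALYs are to be based on the Breast-Q and EQ-5D. The section also says "Because costs and effects will be measured over multiple years, both costs and effects will be discounted at the rate of 3.5" percent.

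The comparison group is described in three places:

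- Section 8.4: "For comparison assessment, this survey will be administered to an additional 45 patients undergoing standard of care hypofractionated radiation". On timing, it adds: "The Health Care Expense Survey should be provided to the patient and completed by the patient 2-8 weeks post standard of care hypofractionated radiation". As to selection, the group is drawn from people "who are otherwise not eligible or interested in enrollment on this protocol", and the matching is limited to two factors: "This comparison cohort will be case-matched for distance to treatment facility and employment status".
- Section 7, calendar footnote 12: "Identified patients who voluntarily agree to complete the Health Care Expense Survey should be provided this survey at 2-8 weeks" after standard hypofractionated treatment. Footnote 13 and section 12.1 tie the consent letter to that survey alone.
- Section 2.6: costs of 45 de-identified patients treated with a standard hypofractionated regimen of 19 treatments. Direct costs come from institutional financial and claims data and are analysed with generalized linear models.

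**The concern.** An ICER divides a cost difference by an effect difference, and net benefit values the same effect difference in money. Both need an effect estimate in each group. The plan collects utilities in trial patients and describes only cost collection in the comparison patients. Followed as written, it would reach the analysis with no comparator term for effect.

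At stake is the QALY half of one secondary objective. If the gap is filled only once results are available, the direction of the effect difference would rest on a source that the protocol never fixed.

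**Working it through.** No sample size or power figure is at issue, so the check traces each required input to its data source in each group.

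**Formulas.** With C for cost, E for effect, d for the between-group difference and L for willingness to pay:

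- ICER = dC / dE
- Net benefit: INB = L x dE - dC
- Var(INB) = L^2 x Var(dE) + Var(dC) - 2L x Cov(dE, dC)

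For independent groups, Var(dE) and Cov(dE, dC) are each the sum of a trial term and a comparison term.

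**Trace of the five inputs in section 9.2.4.**

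1. Mean cost difference: available (survey and claims, both groups).
2. Variance of the cost difference: available.
3. Mean effect difference: trial patients only.
4. Variance of the effect difference: trial term only.
5. Covariance: trial term only. The comparison term needs cost and utility from the same patients.

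Three of the five lack comparator data. In forms, the EQ-5D is planned before RT and 2-8 weeks after: 102 x 2 = 204 in trial patients at most, against 45 x 0 = 0 in the comparison group.

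**Other possible utility sources.**

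- The expense survey (Appendix II) asks about employment, travel, lodging, accompaniment, days off work, child care and wages. It has no health-state question.
- Section 8.4 cites Appendix IV, the EQ-5D, but in the sentence about the weekly diary. The paragraph on the 45 patients names only the expense survey.
- Published Breast-Q results serve the comparison in section 9.2.1. They are 0-100 scale scores (section 8.2), not utilities, and no mapping is stated.
- The institutional research database is assigned to toxicity and recurrence (sections 9.2.2 and 9.2.3).

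**Sensitivity to the missing terms (every value assumed; the documents give none).** Take a saving of USD 5,000 and a post-RT utility difference between -0.05 and +0.05, reached linearly over 10 weeks.

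- dE = 0.5 x 0.05 x 10/52 = 0.0048 in absolute value.
- The ICER is about +USD 1.04 million per QALY at one end and -USD 1.04 million at the other, and undefined at zero.
- With L = USD 100,000, INB runs from USD 4,519 to USD 5,481.

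The ICER is therefore unstable, while net benefit over a short horizon moves much less. For its standard error, assume a cost SD of USD 3,000, a QALY SD of 0.02, groups of 87 and 45, and zero trial-group covariance. The standard error is USD 552, 662 or 756 when the comparison group's cost-effect correlation is +0.5, 0 or -0.5.

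**Precision if the EQ-5D were added.** The 95% half-width for the utility difference is 1.96 x SD x sqrt(1/n + 1/45).

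- n = 102: 0.351 SD. n = 87: 0.360 SD.
- For an assumed SD of 0.10 to 0.25: 0.035 (0.10, n = 102) to 0.090 (0.25, n = 87).

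This treats the groups as independent and ignores the case-matching.

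**Time frames side by side.**

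- Charges (section 8.4): registration to 2-8 weeks after RT.
- EQ-5D: before RT and 2-8 weeks after.
- Lost work (Appendix II): to 40 days after RT.
- Diary (Appendix III): to 6-10 weeks after RT, although the survey it supports is completed by week 8.
- Breast-Q: to 24 months.
- Cost models (section 2.6): include time on study, with no end date.
- Section 9.2.4: costs and effects over several years, discounted.

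These do not describe one common horizon.

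**The case against.** The strongest reply is that this is missing detail in an analysis called exploratory. Objective 1.2.4 allows historical controls, and a Monte Carlo model can take its parameters from outside the trial, so naming a source might close the gap. This stands in part: external utilities are not ruled out. But the plan names no dataset, time point or covariance assumption. Summary utilities from elsewhere could give a mean and a variance, but not a patient-level covariance with the costs of these 45 patients.

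Three stronger readings are tempting and go beyond the text:

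- *That comparator utilities will be picked after results are seen.* The documents leave the source open; they do not say when it will be chosen.
- *That the discounting sentence is simply wrong because all measurement is short.* The claims data in section 2.6 have no stated end date, section 9.2.4 plans side-effect costs, adverse events are recorded to year 3 (section 12.4.1), and the Breast-Q reaches 24 months. The passages conflict, but the text does not show that only short windows were intended.
- *That the wrong comparator is used.* The ICER formula contrasts hypofractionated with standard fractionation, whereas sections 2.6 and 8.4 make clear that the comparison patients receive standard hypofractionation. This is a labelling fault.

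It is also fair that adding the EQ-5D gives limited information: one post-treatment value, no baseline, in patients who were ineligible or not interested.

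**Conclusion.** The point holds for the QALY part of secondary objective 1.2.4. From the data planned, the effect difference, its variance and the covariance cannot be obtained, so neither can the ICER, net benefit, acceptability curve or probabilistic sensitivity analysis. This rests on reading sections 7, 8.4 and 12.1 together as giving the 45 patients the expense survey as their only questionnaire, which the text supports.

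A reader might infer that the whole economic objective fails. It does not: survey and claims costs exist for both groups, and section 2.6 already specifies a model for direct costs. The primary endpoint, toxicity, recurrence and stopping rules are untouched. Because the affected analysis is secondary and exploratory, severity is minor to should-fix.

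**What to change.** The documents do not say how many of the 45 have already been surveyed, and that decides the route.

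**If comparison patients remain to be surveyed:**

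- Add the EQ-5D-3L to their existing 2-8 week contact, after checking that the consent letter covers it (its wording is not in the text).
- Analyse incremental net benefit, which section 9.2.4 already permits, over one stated horizon common to both groups.
- State the EQ-5D value set and the willingness-to-pay range, and adjust for available characteristics.

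The cost is one short self-completed form. The limitations to declare are the missing baseline utility and residual confounding. Matching covers only distance and employment, and the group may include patients excluded under 4.2.8 for chemotherapy before RT.

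**If they have already been surveyed**, do one of two things, each a change of wording:

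- restate the QALY part of 1.2.4 and 9.2.4 as the cost comparison of section 2.6; or
- name, before analysis, an external utility source, its time point, a covariance assumption and sensitivity ranges.

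**In either case:**

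- Do not use the Breast-Q as a QALY source without a stated mapping to utility.
- Reconcile the charge window in section 8.4 and the EQ-5D schedule with the multi-year and discounting sentence in section 9.2.4 and with time on study in section 2.6.
- Label the ICER comparator as the standard hypofractionated regimen of sections 2.6 and 8.4.

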## **8.5 Safety**

Routine safety and tolerability will be evaluated from the results of reported signs and symptoms, scheduled physical examinations, vital sign measurements, and clinical laboratory test results. More frequent safety evaluations may be performed if clinically indicated or at the discretion of the investigator.

### Physical Examination

Complete and symptom-directed physical examinations will be performed by a licensed physician (or physician's assistant or nurse practitioner).

### Vital Signs

Vital signs (blood pressure, respiratory rate, pulse rate and temperature) will be obtained.

## **8.6 Stopping Rules**

After 45 patients have been enrolled and followed for 6 months, an interim analysis will be performed of all patients with greater than 6 months of follow up. Based on an expected RT toxicity rate of  $\leq 10\%$ , if greater than 20% of our patients are found to have

Protocol name: NOVEMBER (Novem- (9), BrEast Radiation), A Phase II trial of a 9 day course of whole breast radiotherapy for early stage breast cancer.

Version Date: 23NOV2021

Principal Investigator: [name]

non-acute grade 2 or 3 RT toxicities  $\geq$  6 months after the completion of radiation, this study will be temporarily halted for interim review. Based on an anticipated recurrence rate of < 7%, if  $\geq$  15% of patients have a documented local recurrence, this study will be temporarily halted for interim review. Once temporarily halted, a team of experts will review the data to determine if it is safe to proceed with the trial or if the trial should be discontinued.

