## 2.2 Baseline Toxicity from whole breast radiation

In reviewing toxicity data from previous hypofractionation trials, the UK STARTB 40Gy in 15 fraction treatment arm (majority received an optional 10Gy boost) reported a 5 and 10 year local recurrence rate of 2% and 3.8% (respectively), and 10 year 4.3% local-regional relapse (3.2-5.2%, CI). Reported toxicities are shown in the table below. Cosmetic results overall were better in the 3 week 40Gy hypofractionation arm compared to the 5 week 50Gy standard arm.

Symptomatic rib fracture	2.2%
Lung fibrosis	1.7%
Ischemic heart disease	1.5%
Breast edema	5%
Telangiectasia	4.2%
Breast shrinkage	26%
Breast induration	14%

In the NCIC hypofractionation randomized study the local recurrence rate (invasive only) at 5 and 10 years was 2.8% and 6.2%. Grade 3 RT associated morbidity was 4%. 30% of women had less than an excellent or good cosmetic result (grade 2 or 3 on the EORTC photographic assessment). This slight higher recurrence rate compared to the UK start data may reflect a higher risk group or the fact the NCIC patients did not receive a lumpectomy cavity boost.

Based on this information, we feel that a reasonable expected combined radiation grade 2 or greater non-acute toxicity rate (non-cosmetic) would be 7-10%, a conservative estimate from several prospective trials.

Also based on this information, we feel that a reasonable expected local recurrence rate would be 5-6%, with an upper limit of 10% acceptable.

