### **3.4 Study Duration**

We anticipate enrolling 30 patients per year on this trial with 3 years of clinical follow up. We plan to do a chart review at 5 years for any long-term toxicities or evidence of late breast cancer recurrences.

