### **12.3 Data and Safety Monitoring Plan**

A Data and Safety Monitoring Committee (DSMC) is established at Huntsman Cancer Institute (HCI) and approved by the NCI to assure the well-being of patients enrolled on Investigator Initiated Trials that do not have an outside monitoring review. Roles and responsibilities of the DSMC are set forth in the NCI approved

plan. The activities of this committee include a quarterly review of adverse events including SAEs, important medical events, significant revisions or amendments to the protocol, and approval of cohort/dose escalations. If the DSMC and/or the PI have concerns about unexpected safety issues, the study will be stopped and will not be resumed until the issues are resolved. The DSMC also reviews and approves audit reports generated by the Research Compliance Office.

All **phase II** studies are reviewed by the full committee at each quarterly DSMC meeting. This includes a review of all serious adverse events (SAEs) occurring in patients treated at HCI or its affiliates as well as all grade 3 or greater toxicities for patients on treatment and within 30 day follow-up window (only if possibly, probably or definitely related).

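### The numeric late-toxicity trigger in section 8.6 is applied only once, at 45 patients; repeating it at the quarterly DSMC meetings until accrual ends is a cheap improvement

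*Combined protocol and SAP*

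**What the plan says.** Section 8.6 (Stopping Rules) plans one look, timed as "After 45 patients have been enrolled and followed for 6 months"; it takes in everyone whose follow-up exceeds 6 months at that time. The reference rate is at most 10% ("Based on an expected RT toxicity rate of"). This agrees with section 2.2, whose expectation for events of grade 2 or higher reads: "non-acute toxicity rate (non-cosmetic) would be 7-10%, a conservative estimate from several prospective trials". The trigger is strict, worded as "if greater than 20% of our patients are found to have" the event in question. That event is described as "non-acute grade 2 or 3 RT toxicities", counted from 6 months after radiation onward. Its consequence is a temporary halt and expert review, not termination. No later look against this limit is described, and no operating characteristics are given.

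Other sections bear on the point:

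- Section 3.4: "We anticipate enrolling 30 patients per year on this trial". Section 3.2 sets enrolment at 102.
- Section 12.3: phase II "studies are reviewed by the full committee at each quarterly DSMC meeting". The review it itemises covers SAEs and related grade 3 or greater toxicity on treatment and within 30 days. The same section also refers to a general quarterly review of adverse events, and lets the DSMC or the principal investigator stop the study over unexpected safety issues. No numeric boundary is attached to that power.
- Section 12.4.1: adverse events of all grades are recorded until year 3. The study calendar (section 7) schedules assessments at 6 and 12 months and at 2 and 3 years.

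**The concern.** Late effects are a stated secondary objective (1.2.2) and the subject of the protocol's own halting rule. When the single look takes place, about 15 patients have been enrolled but lack 6 months of follow-up, and about 42 have not been enrolled. None of these 57 patients ever enters a comparison with the 20% limit. Events that first appear in the first 45 after the look do not enter one either. If the true rate is too high and the single look happens to fall under the limit, accrual continues with no further numeric check, although the committee meets every quarter and the events are being recorded anyway.

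**Working it through.** The plan states no error rates for this rule, so there is no figure of its own to reproduce.

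**Inputs.** First look at 45 patients, strict limit of 20% and expected rate of at most 10% (8.6); 30 patients per year (3.4); 102 enrolled (3.2); quarterly meetings (12.3).

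**Timing.** 45/30 = 1.5 years to enrol 45 patients, plus 0.5 year of follow-up, gives 2.0 years. Enrolment by then is 30 × 2.0 = 60, leaving 102 − 60 = 42. Accrual ends at 102/30 = 3.4 years. The short time from enrolment to the end of radiation is ignored.

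**Single look.** More than 20% of 45 means at least 10 events, so P(halt) = P(Bin(45, p) ≥ 10).

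**Repeated looks.** Patients with 6 months of follow-up at time t number 30 × (t − 0.5). Quarterly meetings from t = 2.0 until accrual ends give 45, 52, 60, 67, 75 and 82 patients. The halting counts are 10, 11, 13, 14, 16 and 17 events. P(halt at any look) comes from an exact sequential binomial recursion; a simulation of 400,000 trials gave 61.8% at p = 20% and 1.9% at p = 10%.

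| True rate | Single look at 45 | Quarterly looks, 45 to 82 |
|---|---|---|
| 10% | 1.2% | 1.9% |
| 15% | 12.7% | 21.1% |
| 20% | 41.2% | 61.9% |
| 25% | 72.0% | 90.4% |
| 30% | 90.7% | 98.8% |

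**Where the gain arises.** At a true 20%, the cumulative halt probability over the six looks is 41.2%, 50.0%, 53.1%, 57.3%, 59.1% and 61.9%. The first added look supplies 8.8 of the 20.7 points.

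**Sensitivity.**
- Size of the first look: with 46, 47, 48 or 49 patients the trigger is still 10 events, and the single look halts 44%, 47%, 50% or 53% of the time at a true 20%.
- Accrual: at 20, 25, 30, 34 and 40 patients per year, quarterly looks halt 62%, 65%, 62%, 63% and 56% of the time at a true 20%.
- Starting point: applying the raw limit quarterly from about 15 patients raises halts at a true 10% to about 9.7%, and from about 7 patients to about 19%.

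**Patients spared.** Enrolment at the six looks is about 60, 67.5, 75, 82.5, 90 and 97.5. If every halt became permanent, the expected number not enrolled at a true 20% is 0.412 × 42 = 17.3 with one look and 22.3 with six. At a true 30% it is 38.1 and 40.3.

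**The case against.** The strongest reply is that this is a coherent phase II plan: one numeric look, discretionary oversight afterwards, and a trigger that only pauses the trial. Four parts of that reply stand.

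1. A true rate of 20% is the trigger itself, so a strict inequality gives a halt probability near a half whatever the design. A reader might infer from the 41% that the plan's limit goes largely unenforced. The documents do not support that: the same look halts 72% of the time at 25% and 91% at 30%.
2. A reader might take the look to be 45 patients seen at 6 months only. Section 8.6 includes every patient with more than 6 months of follow-up and counts toxicity at 6 months or later. At the stated pace the first patients have almost 24 months by then and the average is about 15, so some later-emerging toxicity is already counted.
3. A reader might infer that there is no safety oversight after the look. Section 12.3 leaves a general power to stop, which the 41% does not count.
4. The benefit in patients is modest, about 2 to 5 fewer enrolled between true rates of 30% and 20%. A halt at the last look spares about 5.

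It would also go too far to say that the DSMC already has the needed data before it. The itemised quarterly review does not name late grade 2 events, and section 11 promises data review no less than annually.

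What the reply does not remove is the gain above the limit. At a true 25% the numeric rule misses 28% of the time with one look and about 10% with repeated looks. Discretion over unexpected safety issues is not a substitute for a limit that the protocol has already chosen.

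**Conclusion.** The point holds as a low-cost improvement, not as an error or contradiction in the plan. The numeric late-toxicity rule operates once, near month 24, and not during the enrolment of the remaining 42 or so patients. Repeating it quarterly while accrual is open raises the chance of a halt by about 21 points at a true 20%, 18 at 25% and 8 at 30%.

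The price is 0.7 points at the expected 10%, but 8 points at a true 15%, which is above expectation and below the limit. The claim that false halts barely increase therefore applies to the expected rate only.

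These figures assume exactly 45 patients at the first look, 30 patients per year, looks only while accrual is open, and one fixed probability of late toxicity per patient, counted once 6 months is reached. Events that emerge later would add to detection under repeated looks. All figures describe the numeric trigger alone.

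**What to change.** Keep the trigger, the first look at 45 patients, and the temporary halt with expert review. Add to section 8.6 that, from that look until accrual ends, the same cumulative proportion among all patients with more than 6 months of follow-up is tabulated for each quarterly DSMC meeting and compared with the same limit. Add to section 12.3 that the DSMC report includes late grade 2 events. State that repeated looks do not begin before 45 patients, and give the operating characteristics of the rule.

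The cost is a few lines of text and one table per meeting, from events that section 12.4.1 already requires to be recorded. The statistical cost is the extra temporary halts shown above, mainly when the true rate lies between the expected rate and the limit.

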#### **5.5 Duration of Therapy**

Subjects must be withdrawn from the study treatment for the following reasons:

- Subject withdraws consent from the study treatment and/or study procedures. A subject must be removed from the trial at his/her own request or at the request of his/her legally acceptable representative. At any time during the trial and without giving reasons, a subject may decline to participate further. The subject will not suffer any disadvantage as a result.
- Subject is lost to follow-up.
- The development of a second cancer or recurrent disease.
- Death.

Subjects may be withdrawn from the study for the following reasons:

- The subject is non-compliant with radiation treatments, trial procedures, or both; including the use of anti-cancer therapy not prescribed by the study protocol.
- If, in the investigator's opinion, continuation of the trial would be harmful to the subject's well-being.
- Development of an intercurrent illness or situation which would, in the judgment of the investigator, significantly affect assessments of clinical status and trial endpoints.
- Deterioration of ECOG performance status to 4.

Protocol name: NOVEMBER (Novem- (9), BrEast Radiation), A Phase II trial of a 9 day course of whole breast radiotherapy for early stage breast cancer.

Version Date: 23NOV2021

Principal Investigator: [name]

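### The local-recurrence halt trigger counts only patients with more than 6 months of follow-up, so a recurrence in a patient whose follow-up ends earlier is lost from the rule

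*Combined protocol and SAP*

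**What the plan says.** Section 8.6 (Stopping Rules) sets one interim look. It is timed "After 45 patients have been enrolled and followed for 6 months", and at that point "an interim analysis will be performed of all patients with greater than 6 months of follow up". Two triggers follow.

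- **Toxicity:** a halt "if greater than 20% of our patients are found to have" non-acute grade 2 or 3 radiation toxicity at or beyond "6 months after the completion of radiation, this study will be temporarily halted for interim review".
- **Recurrence:** against an anticipated rate below 7%, if at least 15% of "patients have a documented local recurrence, this study will be temporarily halted for interim review". No time limit is attached to this event.

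Section 8.6 does not say how a patient who leaves before 6 months is counted.

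Section 5.5 (Duration of Therapy) has two lists. The mandatory list is headed as withdrawal from study treatment and includes "The development of a second cancer or recurrent disease". The discretionary list is headed as withdrawal from the study and includes "If, in the investigator's opinion, continuation of the trial would be harmful to the subject's well-being". The Study Schema plans clinic visits for 3 years or until death. Section 8.3 collects recurrence data at 6, 12, 24 and 36 months, with a chart review at 5 years. No section says whether follow-up continues after a section 5.5 withdrawal.

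**The concern.** An interim safety set should be fixed by something that cannot depend on the outcome being monitored, such as time since treatment ended. Section 8.6 fixes it by follow-up attained. For recurrence the two can be linked: a patient who recurs early may die, withdraw consent, move her care elsewhere, or be taken off study by a site that reads section 5.5 as a list of off-study criteria. Her recurrence is a genuine event under the trigger, yet she does not belong to the set to which the trigger is applied.

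Section 8.6 contains the trial's only numeric safety thresholds. If recurrence were well above expectation, the events most likely to be missing are the earliest ones.

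**Working it through.** **Inputs.** From section 8.6: look after 45 patients, recurrence threshold at least 15%, anticipated recurrence below 7%, toxicity threshold above 20%. From section 2.2: expected local recurrence 5-6%, with 10% the upper acceptable limit. Assumed, because the documents give no figure: the number or share of recurrences that are early and lost to the set.

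**The rule as it stands.** The plan states no error rate or power for the interim rule, so there is no figure to reproduce. For 45 patients, 0.15 × 45 = 6.75, so 7 recurrences are needed (7/45 = 15.6%). Exact binomial chance of 7 or more among 45:

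| True recurrence rate | P(halt) |
|---|---|
| 7% | 0.036 |
| 15% | 0.52 |
| 20% | 0.82 |
| 25% | 0.96 |

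**Direction.** Removing one patient who has the event changes x/n to (x − 1)/(n − 1), which is smaller whenever x < n. Each excluded early recurrence therefore lowers the observed rate.

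**By count, 45 treated, k early recurrences excluded.** The number still needed among the remaining 45 − k is the smallest integer at or above 0.15 × (45 − k).

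| k | Remaining | Still needed | Largest total that does not halt |
|---|---|---|---|
| 0 | 45 | 7 | 6 of 45 (13.3%) |
| 1 | 44 | 7 | 7 of 45 (15.6%) |
| 2 | 43 | 7 | 8 of 45 (17.8%) |
| 3 | 42 | 7 | 9 of 45 (20.0%) |

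The last row is the illustration: 9/45 = 20.0% halts if everyone counts, while 6/42 = 14.3% does not. If the look instead waits for 45 patients who have passed 6 months, the pattern is the same: 6/45 = 13.3% does not halt, and (6 + 3)/(45 + 3) = 9/48 = 18.8% does.

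**By probability.** Let f be the share of recurrences that are early and excluded. Early exclusions are Binomial(45, p·f). The rule is then applied to those remaining, with event probability p(1 − f)/(1 − p·f).

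| True rate p | f = 0 | f = 0.10 | f = 0.25 | f = 0.50 |
|---|---|---|---|---|
| 15% | 0.52 | 0.41 | 0.24 | 0.06 |
| 20% | 0.82 | 0.72 | 0.53 | 0.22 |
| 25% | 0.96 | 0.91 | 0.78 | 0.45 |

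The range of f is an assumption. At the anticipated ceiling, 0.07 × 45 = 3.15 recurrences are expected in total, and few of these should fall before 6 months.

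**Toxicity trigger, for contrast.** The event must be present at 6 months or later, so a patient not seen to that point holds no qualifying event. Leaving her out removes a non-event: 9/45 = 20.0% does not exceed the threshold, but 9/44 = 20.5% does. With 42 patients past 6 months, a true rate of 20% and 3 early leavers, P(halt) is 0.47 if the leavers are excluded (9 of 42 needed) and 0.32 if they are kept as non-events (10 of 45 needed).

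**The case against.** The strongest reply is that section 5.5 does not take a patient with recurrence out of follow-up. Its mandatory list concerns study treatment, which is 9 fractions over 11-14 calendar days. By month 4 there is no treatment to withdraw from, and the Study Schema ends visits only at 3 years or death. This largely stands. A reader might infer that every early recurrence is dropped from the rule, and the documents do not support that. Exclusion occurs only if follow-up actually ends.

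The reply does not close the gap. The same list includes loss to follow-up and death, and says that a subject must be removed from the trial at her own request, so a site could apply it as off-study criteria. Death, withdrawn consent and loss end follow-up on any reading.

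A second reply is that early local recurrence should be rare. Section 2.2 cites 2% at 5 years in the UK 15-fraction arm. This stands and limits the size of the point, although a halt rule exists for the case in which the expected rate is wrong.

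A third is that the monitoring committee reviews adverse events quarterly (section 12.3) and the study is stopped if there are concerns about unexpected safety issues. That is a real safeguard, but it has no numeric threshold and does not name recurrence.

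**Conclusion.** The point holds for the local-recurrence trigger only. Its event is open in time, but its analysis set requires more than 6 months of follow-up, so a documented recurrence in a patient who exits earlier is lost and the trigger is biased toward not halting. Under assumed counts, one to three such losses let 7 to 9 recurrences among 45 treated patients (15.6% to 20.0%) pass without a halt. At a true 20% rate, P(halt) falls from 0.82 to 0.72 if a tenth of recurrences are lost. The size rests entirely on the assumed number of early losses, which is expected to be small.

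A reader might also infer that the toxicity trigger is weakened in the same way, or that excluding early leavers can only lower an observed rate. Neither follows. Late toxicity is defined at 6 months or beyond, early leavers hold no such event, and excluding them can raise that rate. The toxicity trigger would lose an event only if a leaver went on to develop or keep a late effect, on which the documents give no information. Counting an unresolved effect at month 4 as late would redefine the endpoint.

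**What to change.** In section 8.6, for the recurrence trigger:

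- Define the interim set as all treated patients whose radiation ended at least 6 months before the data cut, whatever follow-up they attained.
- Count a documented local recurrence at any time after radiation.
- Report the number of early exits and their reasons beside the interim result.

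Reconcile section 5.5 with the Study Schema so that it is clear whether follow-up continues after each kind of withdrawal. Leave the toxicity trigger's event definition unchanged.

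The cost is a few sentences; recurrence data are already collected. The downside is a slightly higher chance of a temporary review, which does not itself end the trial. Early leavers without recurrence would now stay in the denominator as event-free. With 45 treated this is harmless for up to four of them, because 7 recurrences are needed at every size from 41 to 45. With five, the number needed would be 7 of 45 instead of 6 of 40, which is a further reason to report early exits.
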